General statistical details: Age and sex will be treated as covariates of no interest in all statistical analyses. Intracranial volume (computed by Freesurfer) will also be used as a nuisance covariate in morphometry analyses to control for size-related variance. Residual effects of motion on functional connectivity estimates will be tested post hoc by regressing individuals' frame-to- frame motion against

functional connectivity beta values ⁵⁵. Potential effects of impulsivity, depression, anxiety, and sleep on outcomes will be explored in post hoc sensitivity analyses.

Behavioral Data Analysis:

PhenX Toolbox Monetary-Choice Questionnaire⁴³: The protocol is scored by calculating where the respondent's answers place him or her amid reference discounting curves; placement amid steeper curves indicates higher levels of impulsivity. Subject-specific discounting rates will be entered into MATLAB ANCOVA models testing group differences.

PhenX Toolbox The Iowa Gambling Test^{TM 4}: Total winnings and the ratio of high vs. low risk gambles will be entered into MATLAB ANCOVA models testing group differences.

MRI Analyses: Analyses for primary hypothesis testing will employ a region of interest (ROI) approach. ROIs in VMPFC, orbitofrontal cortex, and the striatum will be used in structural and functional neuroimaging analyses. Cortical ROI definitions will be based on the Human Connectome Project multi-modal parcellation atlas [81]; subcortical ROIs will be based on Freesurfer automated parcellations. ROI analyses will be considered significant at the two-tailed alpha of $p < .05$ after Bonferroni-correction for the number of ROI comparisons. We may also conduct exploratory voxel-level fMRI analyses. These analyses will be corrected for multiple comparisons by applying a voxel-height threshold of $p < .001$, and a cluster-size threshold of $p - \text{FDR} < .05$ to all second-level models.

Grey matter comparisons between Veterans exhibiting STBs and matched controls.

Cortical thickness and grey matter volume (as computed by Freesurfer) will be extracted from the VMPFC and striatum. Measures will be compared between Veterans with STBs and matched controls to test the hypothesis that these metrics are reduced in Veterans with STBs.

Differences in white matter integrity between Veterans with STBs and controls.

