Deterministic tractography of diffusion data will be conducted with DSI Studio (<http://dsi-studio.labsolver.org/>). The generalized q-sampling algorithm will be used for fiber reconstruction. This algorithm permits estimation of multiple fibers per voxel improving reconstruction accuracy in areas rich in crossing fibers [82]. Fiber streamlines will be estimated from "seed" ROIs and then filtered to exclude streamlines passing through, but not ending in, target ROIs. If the seed is in striatum, targets will be located in VMPFC/orbitofrontal cortex, or vice versa. To test the hypothesis that white matter pathways connecting VMPFC-to-striatum are compromised in Veterans with STBs, individual-level track statistics (anisotropy, density) will be entered into MATLAB ANCOVA models.

Differences in fMRI activation during decision-making between Veterans with/out STBs.

These analyses test the hypothesis that neural signals in the striatal-to-VMPFC circuit related to rewards and decision-making are attenuated in Veterans with STBs. Preprocessed fMRI data from the reward expectancy task will be used for these analyses. Whole-brain first-level fixed-effect GLMs will be constructed for each subject with SPM12. A parametric regressor will be used to model univariate fMRI activation related to reward expectancy.

Parametric values are set to +0.5 for probable wins, -0.375 for probable losses, +0.125 for ambiguous cues, and zero for the neutral cues (see D5.5.2) [83]. Separate regressors for positive (better than expected) and negative (worse than expected) prediction errors will also be constructed. GLMs will be created by convolving the canonical hemodynamic response function with regressors of interest and nuisance regressors (motion parameters and derivatives, mean signal in cerebrospinal fluid). Subjects will be treated as random effects in second-level univariate fMRI models. To evaluate whether reward-related signals are blunted in Veteran with STBs, the averaged blood oxygen level-dependent (BOLD) signal for our conditions of interest will be extracted from VMPFC and striatal ROIs and contrasted between groups. Whole-brain statistical maps for reward expectancy and prediction errors will also be contrasted between Veterans with STBs and controls.

Statistically significant clusters from this univariate whole-brain analysis may be used as ROIs in functional connectivity models below.

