Differences in functional connectivity between Veterans with STBs and controls.

These analyses test the hypothesis that the VMPFC-to-striatal decision-making circuit is less functionally cohesive in Veterans with STBs. Functional connectivity analyses of both task (reward expectancy) and resting-state will be conducted using the CONN Toolbox.⁵⁰

Unsmoothed residual BOLD time courses will be extracted from each subjects' preprocessed data and then cross-correlated. The resulting correlations will be converted to z-scores via Fisher's R-to-Z transformation in order to improve conformation to the assumptions of the GLMs used for seed-based hypothesis testing. Z-scores will be entered into GLMs comparing VMPFC-to-striatal connectivity between groups. For task-based functional connectivity, a weighted GLM approach will be used to compare connectivity during the expected reward and prediction error task conditions of between Veterans with and without STBs. Additional analyses using ROIs functionally-defined in the univariate analysis described above as seeds may also be run.

Design Considerations & Alternative Outcomes: This hypothesis testing sequence focuses on the VMPFC-to-striatum decision-making circuit. However, effects may be mediated by regions outside this *a priori* network e.g. in the amygdala-to-VMPFC circuit implicated in bipolar disorder with suicidality [85]. The role of this circuit could be explored should we fail to reject the null hypothesis. Alternatively, a data-driven method such as multi-voxel pattern analysis could be used to functionally identify neural circuits differing between Veterans with and without STBs.

E3.2 Evaluate whether correlates of decision-making and cognitive control indicate risk severity.

Hypotheses: Decision-making will be less risky and/or impulsive in higher- vs. lower- risk Veterans with STBs. Structural and functional integrity of cognitive control regions will be superior in higher-risk Veterans with STBs.

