Differences in white matter integrity between groups. PFC regions involved in cognitive control are anatomically connected to striatum by white matter pathways, e.g. the cortico- striato-thalamic loops². Damage to these pathways may undermine efficient neurotransmission of top-down cognitive control signals which are fundamental for goal- directed behaviors including decision-making⁵. In individuals with STBs, efficiency of the cognitive control system may permit the development of more deliberate suicidal behaviors rather than impulsive attempts. Deterministic tractography statistics will be contrasted between groups to test this hypothesis. Tractography procedures match those used above (*Differences in white matter integrity between Veterans with STBs and controls*). Subjects' track statistics (anisotropy, track density) will be entered into GLMs contrasting high-risk and low-risk Veterans with STBs.

Univariate fMRI differences in inhibitory control. This analysis tests the hypothesis that response inhibition, a component of cognitive control, will be superior in high-risk Veterans relative to their lower-risk Veterans and controls. We anticipate that the fMRI signal in VLPFC during successful inhibition will be strongest in the high-risk group relative to lower-risk Veterans with STBs and controls.

Preprocessed SSRT will be entered into subject-level fixed-effect GLMs constructed with SPM12. Regressors for the following trial types will be constructed: Go trials, Stop Inhibit trials, Stop Respond trials, along with two nuisance regressors (go errors, non- response trials). Stop-Inhibit and Stop Respond trials represent successful, and unsuccessful attempts to halt responses in progress. Null events constitute an implicit baseline. GLMs will be created by convolution of the canonical hemodynamic response function with model regressors. Motion estimates and mean signal in cerebrospinal fluid will also be included as nuisance regressors. Contrasts for each trial type and Stop Inhibit- Stop Respond trials will be included in first-level models. Second-level models where subjects are treated as random effects will be estimated by regressing first-level contrast betas against group. Averaged betas across voxels from ROIs will also be extracted from each subject and contrasted between groups to conduct ROI-level hypothesis tests.

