this naturalistic sample will be more representative of Veterans with STBs. Heterogeneity however, may beget misclassification errors i.e. classification by disorder versus suicidal outcome. The AUC statistic is our planned metric for model comparisons because it easily interpreted. However, AUC metrics can overestimate true performance when applied to a larger dataset where one group is comparatively over-represented i.e. a high AUC is achieved by algorithms optimizing the identification of controls over cases. Alternative performance measures that simultaneously evaluate positive predictive value and sensitivity like precision- recall statistics may be a more robust alternative to AUC.

E3.4.2 Volume-space structural preprocessing. T1-weighted images will undergo intensity normalization, tissue segmentation, and volume-space registration to the Montreal Neurological Institute (MNI)-152 Atlas.

E3.4.3 Surface-space structural preprocessing. T1-weighted images will be resampled to Freesurfer-conformed space, then submitted to intensity normalization, tissue segmentation, spherical registration, volume-space registration to the MNI-152 Atlas. Freesurfer preprocessing also includes surface-space cortical parcellation and volume-space subcortical parcellation.

E3.4.4 General fMRI preprocessing. The following preprocessing steps apply to all fMRI data. Steps include slice-time correction, head motion estimation, realignment, inhomogeneity correction via field map, functional segmentation, registration to MNI-152 space, and an artifact analysis in which high motion volumes (>0.5mm translational or 0.02 rotational motion), or volumes where global signal variance exceeds 3 standard deviations are flagged for nuisance regression in subsequent models. Spatial smoothing with a 4mm full-width, half max Gaussian kernel will be applied to fMRI data subjected to univariate analyses to improve conformation to the assumptions of Random Field Theory.

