E3.4.5 Functional connectivity preprocessing. The following additional subject-level steps carried out with CONN reduce the impact of motion-related artifacts and non-neuronal signal on functional connectivity estimates [100-102]. The anatomical CompCor (aCompCor) routine (implemented in CONN) is an effective method for removing motion-related artefact that does not involve global signal regression [103], a practice that complicates interpretation of correlations [104,105]. Five principal components are extracted from the averaged fMRI signal in each aCompCor compartment (white matter, CSF). Principle components are regressed from subject-level data, along with regressors for linear trend, six estimated motion parameters and their 1st derivatives, and flagged high-motion or high global signal variance time points to limit potential sources of spurious variance. Residuals will be band-pass filtered (high-pass = 0.008, low-pass = 0.15) after confound regression [106].

E3.4.6 Diffusion MRI preprocessing: Preprocessing steps include: eddy-current compensation, head motion estimation and correction, and intra-subject registration. Diffusion preprocessing will be carried out using either FSL or FreeSurfer.

F. PRIVACY, CONFIDENTIALITY, & INFORMATION SECURITY

F1. Privacy interests and confidentiality

Minimizing risk of loss of Protected Health Information (PHI) is a priority of the proposed study. In accordance with VA guidelines and laws of the State of Rhode Island and Providence Plantations, confidentiality of the participants and their information will be upheld as outlined in this document. In agreement with the Department of Veterans Affairs Record Control Schedule 10-1, records will be maintained as outlined in this document. All documentation and data obtained over the course of this study will be stored as outlined in this document.

To protect participants' confidentiality, study participants will be assigned a numerical code that contains no personal identifiers or PHI. Participants will be listed only by this unique participant identification code on data files and data capture forms to maintain their anonymity. Codes will be sequential in numbering, e.g. 7001, 7002, 7003 etc. Identification codes will be applied to all cognitive testing, assessments, health service utilization, and MRI data collected over the course of the study.

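### Motion is cleaned at subject level, but no motion term enters the group connectivity models and the post hoc motion check has no stated consequence

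*Combined protocol and SAP*

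**What the plan says.** **Within each person**, motion control is extensive. E3.4.4 flags volumes above 0.5 mm translation or 0.02 rotation, or with outlying global signal, for nuisance regression. For connectivity, E3.4.5 adds aCompCor: "Principle components are regressed from subject-level data, along with regressors for linear trend, six estimated motion parameters and their 1st derivatives", together with "flagged high-motion or high global signal variance time points to limit potential sources of spurious variance". The first-level models for the reward task (E3.1) and the stop-signal task (E3.2) also carry motion regressors; for the latter, "Motion estimates and mean signal in cerebrospinal fluid will also be included as nuisance regressors".

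**Between people**, the General statistical details of E3.1 state: "Age and sex will be treated as covariates of no interest in all statistical analyses". Intracranial volume is added for morphometry. The E3.1 connectivity paragraph then says "Z-scores will be entered into GLMs comparing VMPFC-to-striatal connectivity between groups" and names no motion term. Whatever motion remains is covered by one sentence: "Residual effects of motion on functional connectivity estimates will be tested post hoc", by regressing each person's frame-to-frame motion against the connectivity values. E3.2 repeats both statements for the attempt v ideation analyses.

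The plan gives no significance threshold for that check, no comparison of motion between groups, no motion limit for excluding a person, and no action if the check is positive.

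**The concern.** The plan itself allows that motion may still affect connectivity after cleaning. Its response is a separate regression run afterwards. If that regression is negative, the group contrast is reported as it stands, although a negative test at this sample size does not show that motion is harmless. If it is positive, the contrast is still unadjusted, and whether and how to adjust would be decided after the results are known.

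At stake is the reading of the connectivity contrasts between Veterans with suicidal thoughts and behaviours and matched controls (E3.1) and between attempt and ideation groups (E3.2). Matching covers diagnosis, age and sex, not motion. Bias needs two conditions together: motion effects that survive the cleaning, and groups that differ in motion.

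**Working it through.** **1. The plan's own figure.** E3.1 (Participant groups) gives 85% power at a total of 72 for an effect of 0.4, three groups and two covariates. With a noncentral F test, df1 = 2, df2 = 72 − 3 − 2 = 67, λ = 0.4² × 72 = 11.52 and α = .05 (assumed, since no alpha is stated there), power is 0.853, and 72 is the smallest total that reaches 85%. The figure reproduces. Two covariates fit age and sex, with no place for motion.

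**2. Set-up for the bias.** The documents give no motion figures, so these are assumptions:
- D: group difference in mean motion, in SD.
- r: within-group correlation of motion with connectivity left after cleaning.
- No true connectivity difference, and a two-sided nominal .05 before Bonferroni correction.
- n per group: 60 v 60, the upper limits in E3.1.

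The unadjusted contrast is then shifted by r × D within-group SD. Its t statistic has noncentrality r × D × √(n/2) on 2n − 4 df (age and sex in the model). For D = 0.5, r = .2, n = 60, this is 0.10 × √30 = 0.548 on 116 df, and the rejection rate is 8.4%.

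**3. False-positive rate, 60 v 60, motion not in the model.**

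| D (SD) | r = .1 | r = .2 | r = .3 | r = .4 |
|---|---|---|---|---|
| 0 | 5.0% | 5.0% | 5.0% | 5.0% |
| 0.3 | 5.3% | 6.2% | 7.8% | 10.0% |
| 0.5 | 5.8% | 8.4% | 12.9% | 19.2% |
| 0.8 | 7.2% | 14.0% | 25.6% | 41.2% |

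With r = 0 the rate is also 5%. Simulation (4,000 runs per setting) agrees: 8.2% at (0.5, .2), 13.4% at (0.5, .3) and 25.5% at (0.8, .3). With each person's motion in the model, the simulated rate is 4.6% to 5.7%, that is, about 5%.

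**4. 30 v 30, the upper limits for attempt v ideation.** The noncentrality becomes r × D × √15. At D = 0.5 this is 0.387 for r = .2 (rate 6.7%) and 0.581 for r = .3 (8.8%). These rates apply to a direct contrast of connectivity. The E3.2 resting-state models instead use connectivity to predict Monetary Choice and Gambling performance, so no rate is given for them. Motion could still enter those models through connectivity.

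**5. What the post hoc check would find.** Approximate power is Φ(atanh(r) × √(N − 3) − 1.96). For N = 120 and r = .2 this is Φ(0.2027 × 10.817 − 1.96) = 0.59; for r = .3 it is 0.92. Simulated at D = 0.5, where the group difference widens the spread of motion a little, the check misses r = .2 in about 38% of studies and r = .3 in about 6%. At N = 60 it misses about 65% and 32%.

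**6. Cost of adding motion.** With a third covariate df2 = 66. Power at 72 is 0.8527 against 0.8530, and the required total stays 72. If groups differ in motion, λ shrinks by 1 − R², with R² = (D²/4)/(1 + D²/4). For D = 0.3, 0.5 and 0.8, R² = 0.022, 0.059 and 0.138, and power at 72 is about 0.84, 0.83 and 0.79. At N = 120 with no group difference in motion (equal-group approximation), power is 0.979 with or without the covariate.

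**The case against.** A reader might infer that the plan controls motion only by a test after the fact. The documents do not support that. Motion parameters, their derivatives and flagged volumes are regressed out before any group model, and the post hoc sentence concerns only what is left.

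A reader might also infer that the contrasts will be biased. Nothing in the documents shows a residual motion effect or a group difference in motion, and matching on diagnosis, age and sex closes some routes to one. At the low end of the range (0.3 SD, .1) the rate is 5.3%, which is negligible.

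The post hoc check is also not idle. At N = 120 it usually detects a residual correlation of .3, so a false-positive contrast that also goes unflagged is uncommon: about 2% of studies at (0.5, .2), and under 0.5% at (0.5, .3) and (0.8, .3). This stands, but it helps only if a flag leads to something, and the plan does not say what. At N = 60 the check is much weaker.

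The tabulated rates are not those of the planned ROI tests, which are Bonferroni-corrected for an unstated number of comparisons. With three, as an assumption, the per-test rate at (0.5, .2) is 3.4% against a nominal 1.7%. The level falls and the inflation stays.

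Finally, a group-level covariate is not the only remedy, since a motion limit for excluding people or matching on motion would also reduce confounding. The plan has neither. A5 lists the baseline comparison with controls as exploratory, and connectivity is one of several modalities in E3.1. That limits the weight of the point but does not remove it.

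**Conclusion.** The point holds in a limited form. Subject-level motion control is good. No per-person motion summary enters the group connectivity models in E3.1 or E3.2, and the post hoc regression neither adjusts the contrast nor has a stated consequence. A motion difference could therefore be reported as a circuit difference, provided that residual motion effects remain and the groups differ in motion.

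The size is conditional on inputs that the documents do not supply. It runs from no inflation, through modest inflation in the middle of the range, to a rate several times nominal when both inputs are large; it is smaller at 30 v 30. The randomised primary outcome is unaffected. Because the measure is already in the plan and the cost is small, the change is worth making before the imaging data are analysed.

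**What to change.** In the General statistical details of E3.1 and E3.2:
- Prespecify each person's mean frame-to-frame motion as a covariate in every group-level connectivity model, including the E3.2 models that use connectivity to predict task performance.
- Report motion by group.
- Show the estimate without the motion covariate alongside the adjusted one.
- Keep the post hoc regression as a diagnostic only.

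The cost is 1 df and no new data, because frame-to-frame motion is already to be used. The loss of power is trivial unless the groups differ strongly in motion. The real downside is that, if motion is partly caused by the trait under study, adjustment may absorb some true signal; that is the reason for showing both estimates.

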The study population will include Veterans 18-75 years old. They will be men or women from the greater Providence area receiving care at the VA who have been discharged from active duty, or who served in the National Guard or reserve units.

Two groups will be recruited. One group will consist of Veterans admitted to the PVAMC psychiatric inpatient unit or medical unit or identified in outpatient settings for suicide attempt or suicidal ideation with any degree of suicide plan, and/or intent to attempt suicide. This group of Veterans may be enrolled into either active or sham TMS+BCBT, if eligible. The second group will consist of DSM-V diagnosis-matched Veterans without current suicidality to act as controls. Controls will also be matched for age ± 5 years, and sex. The control Veterans, if eligible, may be enrolled in the neuroimaging and cognitive battery, and not be eligible to receive the TMS+BCBT intervention. The matching procedure is used to limit the influence disorder-specific characteristics, sex, and age-related brain/cognitive differences on group comparisons. If we are unable to meet annual recruitment goals, sex differences will be handled through statistical covariation and strata for age-matching will be broadened (± 10 years).

D2. Participant Selection:

Participants will consist of Veteran inpatients or outpatients of the Providence VAMC with active suicide ideation or related behaviors, and non-suicidal Veteran controls. The inclusion and exclusion criteria are as follows:

D2.1. Inclusion criteria:

Inclusion criteria for all participants:

- 1) Participants must be Veterans aged 18-75 discharged from active duty, National Guard, or reserves units, receiving care at the VA. They must be able to comply with all study related procedures and visits and be

capable of independently reading and understanding study materials and providing informed consent.

Inclusion criteria for Veterans with suicidal thoughts and behaviors:

- 1) Admission to a hospital or identified in outpatient settings within 2 weeks of suicidal ideation with any methods, intent and/or plans, or within 2 weeks after an attempt as

indicated on hospital chart and confirmed by administration of the Columbia Suicidal Severity Rating Scale (C-SSRS).

Inclusion criteria for non-suicidal Veterans (controls)

- 1) No evidence of current suicidality in the medical record or endorsement of current suicidal thoughts and behaviors on the C-SSRS.

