- 2) Matched to a participant with suicidal thoughts and/or behaviors on DSM-V diagnosis, age \pm 5 years, and sex.

Exclusion criteria:

Exclusion criteria for all participants:

- 1) Primary psychotic disorder (e.g. schizophrenia, schizoaffective disorder)
- 2) Cognitive impairment (as indicated by neuropsychological evaluations and/or diagnoses related to cognitive impairment [e.g., dementia] in the chart)
- 3) Pregnancy/lactation, planning to become pregnant during the study, childbearing potential and does not agree to consistent use of a measure of birth control during the scanning and TMS portions of the study. Confirmation of non-pregnancy among hospitalized patients will be obtained from the medical record review as pregnancy tests are required for psychiatric hospitalization. Pregnancy tests will be administered prior to MRI scanning and/or TMS for control participants or suicidal participants identified outpatient.
- 4) Lifetime history of moderate-to-severe traumatic brain injury.
- 5) Current unstable medical condition.
- 6) Current (or past, if appropriate) significant neurological disorder.
- 7) Lifetime history of: seizures, CNS tumors, stroke, cerebral aneurysm.
- 8) Active moderate-to-severe substance use disorder (within last month, excluding nicotine/caffeine dependencies).

Exclusion criteria specific to TMS+BCBT:

- 1) For safety, participants must meet established screening criteria following MRI safety. MRI involves magnetic fields at similar intensity to those emitted from the TMS stimulation coil. Unless devices are MRI-safe patients may not have:
 - a. Cardiac pacemaker, implanted device (deep brain stimulation) or metal in the brain, cervical spinal cord, or upper thoracic spinal cord
- 2) Other exclusions include conditions that could be worsened by TMS, such:
 - b. Bipolar I disorder or an increased risk of seizures in the case of severe and uncontrolled substance use disorder
- 3) Patients who have previously received Theta Burst Stimulation cannot be enrolled in this study
 - a) The risk of the patient recognizing the difference between active versus the sham would jeopardize the double-blinding framework proposed in this protocol as well as the credibility of reported data.

Exclusion criteria specific to Neuroimaging:

- 1) MRI contraindications (e.g., cardiac pacemaker, non-MRI safe implants, shrapnel, permanent makeup).

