D5.2 EHR variable construction: EHR measures are listed in Table 5. Monthly EHR sums will be averaged by quarter and by year. If categorical variables change over an aggregated time point, the most consistent designation over the analyzed epoch will be used.

Health Services Utilization
Outpatient Visits (any service)
Outpatient Visits (MH service)
Emergency or Urgent Care Visits
Inpatient MH
Inpatient (any service)
Pharmaceutical Utilization
Antidepressant
Antipsychotic
Mood Stabilizer
Anxiolytics
Other medications (non-psychiatric)
Change in Pharmaceutical
Antidepressant
Antipsychotic
Mood Stabilizer
Anxiolytics
Other medications (non-psychiatric)
Mental Health (Current and Lifetime)
Depression
Bipolar disorder
Schizophrenia or schizoaffective disorder
Generalized Anxiety Disorder
Posttraumatic Stress Disorder
Specific Phobia
Panic Disorder
Social Phobia
Personality Disorder
ADHD
SUD
Gambling Disorder
Eating Disorders
Suicidality

Table 5. EHR data extracted at baseline and follow-

E. DATA ANALYSIS

E1. Design and Sample Size

This is a single-site, two-arm RCT with individual participant urn randomization. We propose to randomize 130 Veterans. Approximately 65 will be randomized to active TMS+BCBT and 65 participants will be randomized to sham TMS+BCBT. Recruitment for the intervention will cease once randomization goals are met (i.e. n= ~65 Veterans per condition). Additionally, we will be enrolling 60 Veterans, who will be matched on age (within 5 years), primary psychiatric diagnosis, and sex, for a total of 190 Veterans to be enrolled. A subsample of these veterans (120 in total; one group (n=30) with suicide ideation and another group (n=30) with suicide attempts; and controls (n=60) will be used in the analyses of brain-based biomarkers for suicidality. Veterans will be assessed at the study timepoints outlined in C3. Assessments.

E1.1 Overall Analytic Approach across Aims

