E2.4.1 Statistical power and sample size considerations: As we view tertiary analyses as exploratory and hypothesis generating, we do not present a priori specified sample size or minimum detectable effect size statistics. We have no doubt that we may be underpowered to detect all but large moderation effects. Our inferences will be made cautiously and be guided

by confidence intervals obtained by bootstrap resampling of the observed data.

E3. Aim 2 Analytical Plan (Analyses Related to Cognition and Neuroimaging)

All de-identified data from this study for Aim 2 will be combined with data from subjects who completed neuroimaging procedures in PVAMC IRB protocol #2018-051.

E3.1 Evaluate the relationship between STBs and reward circuits involved in decision-making in Veterans.

Hypothesis: Neural and behavioral correlates of decision-making will differentiate Veterans with STBs from those without STBs.

Rationale: Suicidality is associated with maladaptive decision-making. Neuroimaging in non-Veterans has shown that STBs are accompanied by functional and anatomical differences in the striatal-to-VMPFC reward circuit implicated in decision-making. It is unknown if these potential neurocognitive markers of suicide generalize to Veterans.

Between-group contrasts of decision-making, structural MRI, and functional MRI will be used to test our hypothesis.

E5.1 Participant groups: The STB group will be comprised of Veterans hospitalized for suicide attempt (up to n=30) or suicidal ideation (up to n=30). The diagnosis matched control group is comprised of Veterans (up to n=60) without current STBs. Per power estimations computed with G Power software⁴², 85% power to detect a medium-sized effect of group (0.4) in an ANCOVA model with three groups and two covariates is afforded by a total sample size of 72, or n=24 participants per group. Our enrollment targets exceed this estimate to account for loss of participants that are unable to complete all aspects of the study.

Data sources: Decision-making tasks include the scanned reward expectancy task (card guessing), and the un-scanned Iowa Gambling and Monetary Choice (Delay Discounting) tasks. Structural MRI and diffusion MRI data. FMRI data used in Aim 1 analyses will come from either the card guessing reward task or resting state functional MRI runs.

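### Controls are matched on diagnosis, age and sex, but the E3.1 group tests adjust only for age and sex; if diagnosis predicts the outcome, those tests are conservative and lose some power

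*Combined protocol and SAP*

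**What the plan says.** The control inclusion criterion in D2.1 reads "Matched to a participant with suicidal thoughts and/or behaviors on DSM-V diagnosis, age" (±5 years) and sex. E1 describes 60 further Veterans "who will be matched on age (within 5 years), primary psychiatric diagnosis, and sex". D1 gives the reason: "The matching procedure is used to limit the influence disorder-specific characteristics, sex, and age-related brain/cognitive differences on group comparisons". If recruitment falls short, D1 lets sex be handled as a covariate and the age band widen to ±10 years. It gives no fallback for diagnosis.

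E3.1 then compares groups with ANCOVA or GLM models. For the Monetary-Choice task, "Subject-specific discounting rates will be entered into MATLAB ANCOVA models testing group differences"; for connectivity, "Z-scores will be entered into GLMs comparing VMPFC-to-striatal connectivity between groups". Under General statistical details, "Age and sex will be treated as covariates of no interest in all statistical analyses", and morphometry models add intracranial volume. Impulsivity, depression, anxiety and sleep are left to post hoc sensitivity analyses. Diagnosis appears in neither list, and no pair or matched-set term is named.

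The power statement (the paragraph labelled E5.1, inside E3.1) claims 85% power for an effect of 0.4 "in an ANCOVA model with three groups and two covariates is afforded by a total sample size of 72", that is 24 per group. The targets are up to 30 attempters, 30 ideators and 60 controls.

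**The concern.** Matching on diagnosis removes between-diagnosis variation from the STB-minus-control difference. A model with no diagnosis term leaves that variation in the residual, so the reported standard error exceeds the real one. The test then rejects too rarely under the null and misses some real differences.

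The plan itself expects diagnosis to matter. D1 matches on it for that reason, and the design considerations in E3.3 warn that a transdiagnostic sample may be classified by disorder rather than by suicidal outcome. What is at stake is the sensitivity of the STB-versus-control biomarker comparisons, most of all the Bonferroni-corrected ROI tests.

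**Working it through.** **1. The plan's own figure.** Inputs from the E5.1 paragraph: three groups, two covariates, effect 0.4 (read as f), N = 72. No alpha is given there, so 0.05 is assumed. Then df1 = 2, df2 = 72 − 3 − 2 = 67, and noncentrality f²N = 0.16 × 72 = 11.52. Power from the noncentral F is 85.3%, and 72 is the smallest N that reaches 85%. The stated figure is right.

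**2. Cost of leaving diagnosis out.** Take 60 v 60 (the upper targets, as complete pairs) and unit residual SD. Let rho be the within-pair correlation left after age and sex. The documents do not give rho, so a range is shown.

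- Reported SE = √(2/60) = 0.183.
- Actual SE = √(2(1 − rho)/60), so reported/actual = 1/√(1 − rho).
- Type I error of the planned test ≈ 2[1 − Φ(1.96/√(1 − rho))].
- Power of the planned test = Φ[(d − 1.981 × 0.183)/actual SE], where 1.981 is the t critical value on 116 df.
- Power of a matched test: noncentral t on 59 df, noncentrality d/actual SE.

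Example at rho = 0.2, d = 0.5: actual SE = √(1.6/60) = 0.163. Planned power = Φ[(0.5 − 0.362)/0.163] = 80%. The matched noncentrality is 0.5/0.163 = 3.06, giving 85%.

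| rho | SE ratio | Type I error, planned | Power, planned | Power, matched | Loss (points) |
|---|---|---|---|---|---|
| 0 | 1.00 | 5.0% | 78% | 77% | about 0 |
| 0.1 | 1.05 | 3.9% | 79% | 81% | 2 |
| 0.2 | 1.12 | 2.8% | 80% | 85% | 5 |
| 0.3 | 1.20 | 1.9% | 82% | 90% | 8 |

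E3.1 names three regions (VMPFC, orbitofrontal cortex, striatum) but no ROI count. If three are assumed, alpha is .05/3. Power is then 63.5% v 72.4% at rho 0.2 and 64.4% v 78.8% at rho 0.3, losses of about 9 and 14 points.

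**3. At the plan's own effect.** For two equal groups f = d/2, so f = 0.4 means d = 0.8, and the d = 0.5 above is only f = 0.25. At 60 v 60 and d = 0.8, planned v matched power is 99.6% v 99.8% at rho 0.2. At alpha .05/3 it is 98.5% v 99.1% at rho 0.2 and 99.0% v 99.7% at rho 0.3.

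In the three-group form, adding diagnosis replaces f by f/√(1 − R²) and uses 4 more df (five categories assumed). At N = 120 nominal power is 97.9% without diagnosis and 97.9% to 99.8% with it, for R² from 0 to 0.3. At N = 72 it goes from 85.3% to 85.2%, 88.9%, 92.3% and 95.3% at R² = 0, 0.1, 0.2 and 0.3. These three-group comparisons somewhat overstate the gain, because the nominal figure gives the planned test no credit for diagnosis balance.

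**4. Covariate or pairing?** In a simulation of 60 pairs at d = 0.5 (4,000 runs), with diagnosis explaining 20% of residual variance, the planned ANCOVA reported a mean SE of 0.182 against an actual 0.166. Its type I error was 2.7%. Power was 81.2% as planned, 86.8% with diagnosis added and 85.5% with a paired analysis. With diagnosis explaining 5%, power was 77.2% v 78.9% with diagnosis added. At 0% it was 77.8% planned, 77.7% with diagnosis and 76.4% paired. The covariate recovers the precision without a pair term.

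**The case against.** The case for leaving the plan alone is substantial:

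- Two of the three matching factors are already in every model, so rho reflects mainly diagnosis and may be small.
- At the planned effect and target N almost nothing is lost.
- A5 lists the baseline STB-versus-control difference as exploratory, although E3.1 calls its ROI tests primary hypothesis testing.
- Complete 1:1 pairs are not assured. The power case has 24 controls against 48 Veterans with STBs, all targets are upper limits, and Aim 2 data are pooled with protocol #2018-051, whose matching E3 does not describe.

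All of this stands, and it limits the size of the point. It does not explain why the one matching factor left out of the models is diagnosis.

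A reader might infer four stronger things that the documents do not support:

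- **That power is lost as a matter of fact.** This needs a residual correlation that is nowhere stated; at rho 0 there is no loss.
- **That the tests are biased or give false positives.** While the matching holds, the error runs the other way.
- **That the 85% power is wrong.** It reproduces.
- **That a paired analysis is required.** A strict one could discard unmatched or pooled participants, and in the simulation it did no better than the covariate.

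**Conclusion.** The omission is real and cheap to repair, but it is a modest efficiency point, conditional on diagnosis predicting the outcome. The 2-to-8-point loss for rho 0.1 to 0.3 assumes 60 complete pairs and d = 0.5, and should be read as a sensitivity case for an effect smaller than the planned one. The Bonferroni figures also assume three ROIs. The loss of under one point is for the two-group contrast at d = 0.8 with 60 per group. Attrition toward 72 participants would leave more to gain.

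**What to change.** Under General statistical details in E3.1, add the primary matching diagnosis, in a few pre-specified broad categories, as a categorical covariate beside age and sex. Apply it to every STB-versus-control behavioral, ROI, tract and connectivity model. Keep all participants in the analysis, including those whose match is missing and those pooled from the other protocol; the covariate then also guards against diagnosis imbalance from lost matches or pooling. A matched-set random intercept is optional; if it is wanted, record a matched-set identifier when each control is enrolled.

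The cost is plan wording and a few degrees of freedom (four with five categories). Diagnosis is already collected at baseline, so no new data or participants are needed. If diagnosis does not predict the outcome, nothing is gained and almost nothing is lost.
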